| BMI | Body mass index |
| BP | Blood pressure |
| BUN | Blood urea nitrogen |
| Ca ⁺⁺ | Calcium |
| CBC | Complete blood count |
| CFR | Code of Federal Regulations |
| CHF | Congestive heart failure |
| CI | Confidence interval |
| Cl- | Chloride |
| CL _{cr} | Creatinine clearance |
| C _{max} | Maximum observed concentration |
| C _{min} | Trough observed concentration |
| CNS | Central nervous system |
| CR | Complete response |
| CRF | Case report form |
| CT | Computed tomography |
| CTCAE | Common Toxicity Criteria for Adverse Events |
| CV | Coefficient of variation |
| CYP | Cytochrome P450 |

| Abbreviation or Term ¹ | Definition/Explanation |
|-----------------------------------|---|
| D/C | Discontinue |
| ECOG | Eastern Cooperative Oncology Group |
| eCRF | Electronic case report form |
| DLT | Dose Limiting Toxicity |
| ECG | Electrocardiogram |
| Eg | Exempli Gratia (for example) |
| FACS | Fluorescence-Activated Cell Sorting |
| FDA | Food and Drug Administration |
| FDG-PET | Fluorodeoxyglucose (FDG)-positron emission tomography (PET) |
| GCP | Good Clinical Practice |
| GFR | Glomerular filtration rate |
| GGT | Gamma-glutamyltransferase |
| GLP | Good laboratory practice |
| HBsAg | Hepatitis B surface antigen |
| HBV | Hepatitis B virus |
| HCO ₃ ⁻ | Bicarbonate |
| HCV | Hepatitis C virus |
| HNC | Head and Neck Cancer |
| HIV | Human immunodeficiency virus |
| HR | Heart rate |
| hr | Hour or hours |
| IC ₅₀ | Half maximal inhibitory concentration |
| i.e. | Id est (that is) |
| IEC | Independent ethics committee |
| IND | Investigational New Drug |
| INR | International normalized ratio |
| IRB | Institutional review board |
| IU | International unit |
| IV | Intravenous, intravenously |
| LDH | Lactate dehydrogenase |

| Abbreviation or Term ¹ | Definition/Explanation |
|-----------------------------------|---|
| LLQ | The lower limit of quantitation |
| MedDRA | Medical Dictionary for Drug Regulatory Activities |
| MME | Morphine Milligram Equivalent |
| MRI | Magnetic resonance imaging |
| MRSD | The maximum recommended starting dose |
| MTD | Maximum tolerated dose |
| NOAEL | No-observed-adverse-effect level |
| NOEL | No-observed-effect-level |
| PD | Pharmacodynamic(s) |
| PFS | Progression-Free Survival |
| PK | Pharmacokinetic(s) |
| PO | Per os (administered by mouth) |
| PR | Partial response |
| PT | Prothrombin time |
| PTT | Partial thromboplastin time |
| QC | Quality control |
| RBC | Red blood cell |
| QD | Once-daily |
| QTc | QT interval corrected |
| QTcF | QT interval corrected using Fredericia equation |
| SAE | Serious adverse event |
| SD | Standard deviation or stable disease |
| T _{1/2} | Terminal elimination half-life |
| T ₃ | Triiodothyronine |
| T ₄ | Thyroxine |
| T _{max} | Time of maximum observed concentration |
| TID | Three times daily |
| TSH | Thyroid-stimulating hormone |
| ULN | The upper limit of normal |
| ULQ | The upper limit of quantitation |

Short Title: RESILIENCE

Version Date: 18APR2023

| Abbreviation or Term¹ | Definition/Explanation |
|---|------------------------------------|
| UV | Ultraviolet |
| WBC | White blood cell |
| WOCBP | Women of childbearing potential |
| WONCBP | Women of nonchildbearing potential |

¹ All of these abbreviations may or may not be used in the protocol.

PROTOCOL SIGNATURE

I confirm that I have read this protocol, and I will conduct the study as outlined herein and according to the ethical principles stated in the latest version of the Declaration of Helsinki, the applicable ICH guidelines for good clinical practice, and the applicable laws and regulations of the federal government. I will promptly submit the protocol to the IRB for review and approval. Once the protocol has been approved by the IRB, I understand that any modifications made during the course of the study must first be approved by the IRB prior to implementation except when such modification is made to remove an immediate hazard to the subject.

I will provide copies of the protocol and all pertinent information to all individuals responsible to me who assist in the conduct of this study. I will discuss this material with them to ensure that they are fully informed regarding the study treatment, the conduct of the study, and the obligations of confidentiality.

Note: This document is signed electronically through submission and approval by the Principal Investigator in the University of Utah IRB Electronic Research Integrity and Compliance Administration (ERICA) system.

STUDY SUMMARY

[figure not shown]
| | |
|---|--|
| Title | Effect of Comprehensive Celecoxib Through Treatment for Advanced-Stage Head and Neck Cancer: A Randomized, Double-Blinded, Placebo-Controlled Trial |
| Short Title | RESILIENCE |
| Protocol Identifiers (IRB – internal) | IRB # 124211 |
| IND number | IND Exempt |
| Phase | Pilot |
| Design | Randomized, double-blinded, placebo-controlled |
| Study Duration | 2 years |
| Study Center | Single Site: Huntsman Cancer Institute |
| Objectives | 
Primary Objective: To assess the number of days from surgery to the initiation of radiation with the addition of celecoxib compared to placebo.
 
Secondary Objectives:
 
 - To assess overall pain control and management for patients on celecoxib compared to placebo. - To assess functional outcomes for patients on celecoxib compared to placebo. - To assess the effect of celecoxib therapy on Quality of Life (QoL) compared to placebo. - To assess the average number of treatment days missed during adjuvant radiation for patients on celecoxib compared to placebo. |
| Number of Subjects | 60 |
| Diagnosis and Main Eligibility Criteria | 
Inclusion Criteria:
 
 - Advanced-stage (overall stage III and IV) head and neck cancers (sinonasal, oral cavity, oropharynx, larynx, and hypopharynx) undergoing surgical resection and then adjuvant radiation. - Karnofsky Performance Status of ≥ 70 - Adequate organ function. 
Exclusion Criteria
 
 - Metastatic disease - Exclude patients with chronic kidney disease (stage 4 and 5), prior CVA or acute MI, chronic heart failure, prior episode of GI bleed or stomach or intestinal ulcer, and liver failure. |

Short Title: RESILIENCE

Version Date: 18APR2023

| | |
|-------------------------------------|---|
| | 
- Uncontrolled hypertension- Established in a pain management clinic or has taken opioids regularly for \geq 6 months. |
| Study Product, Dose, Route, Regimen | Celecoxib/placebo 200mg BID oral or via a feeding tube |
| Duration of administration | Celecoxib/placebo will be taken 1 to 7 days prior to surgery until the completion of adjuvant radiation, approximately 4 months total, maximum allowable time on the study is limited to 6 months. |
| Reference therapy | Placebo |
| Statistical Methodology | A mixed-effects regression model that accounts for clustering (patients nested within providers) to compare the average number of days from surgery to the initiation of radiation between treatment and control groups |

SCHEMA

1 OBJECTIVES

1.1 Primary Objective

Recent population-level evidence demonstrates that the number of days from surgery to initiation of adjuvant radiation for advanced-stage head and neck cancer has a strong impact on survival outcomes. Therefore, we seek to assess the number of days from surgery to initiation of radiation with the addition of celecoxib compared to placebo.

Primary Endpoint: The number of days from surgery to the initiation of radiation.

1.2 Secondary Objective

- To assess overall pain control and management for patients on celecoxib compared to placebo.

Secondary Endpoints:

- Subjective pain scores on the visual analog scale of pain intensity averaged over a week at rest, with a swallow, and with a cough.
- Patient satisfaction with pain control questionnaire.
- Narcotic consumption in daily total morphine equivalents averaged over a week.

- To assess functional outcomes for patients on celecoxib compared to placebo

Secondary Endpoints: Current activity level and swallowing capabilities, including food and liquid variety and assessment of G tube utilization.

- To assess the effect of celecoxib therapy on Quality of Life (QoL) compared to placebo.

Secondary Endpoint: completion of quality of life questionnaires EORTC QLQ-H&N43 and MDASI-HN as per the schedule of events.

- To assess the average number of treatment days missed during adjuvant radiation for patients on celecoxib compared to placebo.

Secondary Endpoint: the number of treatment days missed or delayed during adjuvant radiation.

2 BACKGROUND

2.1 Hypothesis

Using celecoxib comprehensively throughout treatment starting 1 to 7 days prior to surgery to the end of adjuvant radiation, will improve pain control, reduce opioid use, and improve QOL and functional status, leading to improved compliance with adjuvant radiation which is known to correlate with improved survival outcomes.

2.2 Head and Neck Cancers

Head and neck cancers (HNC) are defined as squamous cell carcinomas originating in the mucosal surfaces of the upper aerodigestive tract: the oral cavity, pharynx, larynx, nasal cavity, paranasal sinuses, and salivary glands.¹⁰ In the United States, an estimated 51,540 new cases were diagnosed in 2018 with a five-year survival rate of 64.8%.⁹ Successful treatment requires a multidisciplinary approach often combining surgery, radiation therapy, and chemotherapy. 30-40% of patients present with early-stage (stage I or II) disease and can undergo successful surgery and/or external beam or brachytherapy radiation therapy and experience a 70-90% overall five-year survival rate. However, patients with locoregionally advanced disease (stage III/IV) require a combined modality approach often incorporating surgery and postoperative radiation therapy with or without chemotherapy, with reduced overall five-year survival rates of 40-60%.

2.3 The Effect of Pain Control on Overall Survival and Study Objective Rational

Currently, pain control throughout therapy is a major issue for patients with advanced-stage head and neck cancers (sinonasal, oral cavity, oropharynx, larynx, and hypopharynx) undergoing primary surgical resection and then adjuvant therapy. In order to maximize survival outcomes, patients treated with surgery and then adjuvant therapy (ie: radiation or chemoradiation) need to start adjuvant therapy within 8 weeks or approximately 60 days after surgery and need to minimize delays or gaps in adjuvant treatments. A recent NCDB study in this patient population demonstrated 5-year OS differences of 67% versus 52% in these 2 cohorts (initiation of adjuvant therapy <50 days versus >50 days).¹ This has been confirmed in a systematic review and other evaluations of large aggregated national datasets.²⁻⁵ Based on our experience and retrospective examination, we have identified that the leading culprit in these cases is pain management and functional issues. These issues contribute to increased narcotic utilization and reduced recovery after surgery with weight loss, poor oral intake, and reduced overall strength, resulting in delays in initiating adjuvant therapy. This post-surgical condition of the patient is also a significant contributor to missed treatments once adjuvant therapy has begun. Based on retrospective examination, it is estimated a significant percentage of patients do not achieve the recommended rate of compliance.

We recently demonstrated with the addition of celecoxib (a selective COX-2 inhibitor NSAID) in our immediate post-operative pain management pathway that we achieved a statistically significant and clinically meaningful decrease in the amount of opioids utilized while as an inpatient.⁸ The primary outcome of compliance will be analyzed by the average number of days from surgery to the initiation of radiation and adjuvant therapy. In our historical cohort of over 100 recent patients, the mean was 72.8 days (Standard Deviation 16.2 days). Our goal with this intervention is to reduce the days from surgery to radiation to 57.2 days or less because recent population-level data reaffirmed this milestone as significantly improving survival outcomes. Secondary outcomes are subjective pain scores, narcotic use, functional outcomes, and patient QOL and satisfaction with pain control throughout treatment, as well as the average number of days missed during adjuvant therapy. We will study these issues prospectively with monitoring progression through treatment, standardized pain questionnaires, pain score monitoring at each phase through treatment, patient satisfaction with pain, monitoring opioid use, and QOL and functional assessments. We strongly feel that

we can achieve a significant improvement in compliance with adjuvant radiation after surgery and will investigate this medication to achieve that end, which we hope will translate into improved disease-specific and overall survival for our cancer patients.

2.4 Disease group rationale

Patients with advanced-stage head and neck cancers have significant challenges with pain control, opioid utilization, and achieving completion of treatment in a timely fashion. A recent examination of the national cancer database of this population demonstrated that 42% of patients do not start adjuvant radiation within the recommended timeframe (<50 after surgery) and examination of our historical cohorts showed similar findings. Therefore this disease group is an ideal cohort to seek to optimize these parameters, improve pain and quality of life, improve timely cancer care, and improve survival outcomes for our patients.

2.5 Drug selection rationale

Celecoxib has been shown in randomized controlled trials and meta-analysis to improve pain control, decrease opioid use, and improve functional status in patients with chronic inflammatory conditions, such as osteoarthritis and rheumatoid arthritis, thus is a good candidate for our patients.⁶ Decreasing opioid utilization after surgery is clinically significant, as the CDC has shown that dosages of opioids at 50 MME (morphine milligram equivalents) or more per day doubles the risk of overdose and other opioid-related complications.⁷

2.6 Clinical experience

A retrospective matched cohort study of 147 patients who had undergone head and neck cancer surgery with free tissue reconstruction were separated into groups based on celecoxib use in the postoperative setting. Groups were matched by stage and cancer site resulting in 102 patients included, 51 celecoxib and 51 control. Postoperative use of opioids was recorded per patient per day and group mean morphine milligram equivalent was compared. Use of celecoxib was associated with a mean decrease in oral opioid use of 9.9 mg per day (95% CI, -1.2-21.1), an IV mean difference of 3.9 mg per day (95% CI, 1.0-6.8), and a total mean difference of 14 mg per day. The 51 patients who received celecoxib after surgery had a significant decrease in opioid requirements compared to the control group. This is a clinically meaningful difference in decreasing opioid utilization after surgery because the CDC has shown that dosages of opioids at 50 MME (morphine milligram equivalents) or more per day doubles the risk of overdose and other opioid-related complications.⁷

3 DRUG INFORMATION

3.1 Celecoxib

3.1.1 Pharmacology

Celecoxib is a nonsteroidal anti-inflammatory drug that exhibits anti-inflammatory, analgesic, and antipyretic activities in animal models. The mechanism of action is believed to be due to inhibition of prostaglandin synthesis, primarily via inhibition of

cyclooxygenase-2 (COX-2), and at therapeutic concentrations in humans, celecoxib does not inhibit the cyclooxygenase-1 (COX-1) isoenzyme.

3.1.2 Physical and Chemical Properties

Celecoxib is chemically designated as 4-[5-(4 methylphenyl)- 3-(trifluoromethyl)-1H-pyrazol-1-yl] benzenesulfonamide and is a diaryl-substituted pyrazole. The empirical formula is C17H14F3N3O2S, and the molecular weight is 381.38.

Peak plasma levels are reached 3 hours after fasted oral celecoxib dosing with a half-life of 11 hours. Under fasting conditions, both peak plasma levels (Cmax) and area under the curve (AUC) are roughly dose-proportional up to 200 mg BID; at higher doses there are less than proportional increases in Cmax and AUC. With multiple dosing, steady-state conditions are reached by day five with extensive distribution into tissues and about 97% of the drug protein bound.

Celecoxib metabolism is primarily mediated via CYP2C9 ultimately leading to hepatic elimination. Three metabolites, a primary alcohol, the corresponding carboxylic acid, and its glucuronide conjugate, have been identified in human plasma. These metabolites are inactive as COX-1 or COX-2 inhibitors.

3.1.3 Pharmaceutical Properties and Formulation

Celecoxib will be compounded by Investigational Drug Services at Huntsman Cancer Institute into an oral suspension containing either 100 mg or 200 mg of celecoxib, together with inactive ingredients including croscarmellose sodium, edible inks, gelatin, lactose monohydrate, magnesium stearate, povidone, and sodium lauryl sulfate.

Placebo will be identical in appearance to match active counterparts.

3.1.4 Clinical Safety

Celecoxib has been shown to be safe and efficacious in many patient populations and has demonstrated acceptable tolerance. Celecoxib use is contraindicated in patients with renal and hepatic impairment. Celecoxib use can increase the risk of serious gastrointestinal adverse events including bleeding, ulceration, and perforation of the stomach or intestines and older patients with a history of peptic ulcer disease and/or GI bleeding are at higher risk for developing serious GI events. Adverse reactions occurring in $\geq 2\%$ of patients receiving celecoxib from 12 controlled studies in patients with osteoarthritis and rheumatoid arthritis are included in Table 1.

Table 1: Adverse events in $\geq 2\%$ of osteoarthritis and rheumatoid arthritis patients

| Adverse Event | Frequency |
|--------------------------|-----------|
| Gastrointestinal: | |
| Abdominal Pain | 4.1% |
| Diarrhea | 5.6% |
| Dyspepsia | 8.8% |

| | |
|--|-------|
| Flatulence | 2.2% |
| Nausea | 3.5% |
| Body as a whole: | |
| Back Pain | 2.8% |
| Peripheral Edema | 2.1% |
| Injury-Accidental | 2.9% |
| Central, Peripheral Nervous system: | |
| Dizziness | 2.0% |
| Headache | 15.8% |
| Psychiatric: | |
| Insomnia | 2.3% |
| Respiratory: | |
| Pharyngitis | 2.3% |
| Rhinitis | 2.0% |
| Sinusitis | 5.0% |
| Upper Respiratory Infection | 8.1% |
| Skin: | |
| Rash | 2.2% |

4 STUDY DESIGN

4.1 Description

This study is a randomized, double-blind, placebo-controlled, pilot study in which patients will be randomized to receive comprehensive treatment with placebo or celecoxib 200mg twice daily.

4.2 Randomization and Blinding

Patients who meet all criteria for enrollment will be randomly assigned to receive celecoxib (Arm 1) or placebo (Arm 2). Patients will be randomized through the OnCore system in a 1:1 ratio between Arm 1 and Arm 2 and stratified by treating provider.

To preserve the blind, only the Investigational Drug Services Pharmacy personnel at Huntsman Cancer Institute will know treatment assignments. Access to unblinded data/documents will be controlled by the pharmacy to ensure the blind is maintained. Every effort will be made to blind both the patient and the investigator to the treatment assignment, but the inadvertent unblinding of a patient may occur. If an investigator, site personnel, or patient is inadvertently unblinded, the unblinding will not be sufficient cause for the patient to be discontinued from study treatment or excluded from study analyses.

In the case of an emergency, the investigator has the sole responsibility for determining if the unblinding of a patient's treatment assignment is warranted. Patient safety must always be the first consideration in making such a determination. If the treating investigator decides that unblinding is warranted, the investigator should contact the investigational pharmacy for treatment assignment.

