4.3 Number of Patients

A total of 40 evaluable patients will be enrolled in this study with 20 patients randomized to each arm: 20 patients will receive celecoxib and 20 patients will receive placebo. It is expected that 25% of patients who start study therapy and undergo surgery will not start adjuvant radiation. Patients who do not start adjuvant radiation will be replaced. Taking this into account, it is estimated that 53 patients will be randomized to result in 40 evaluable patients.

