12.3 Stopping Rules

While an interim analysis is not planned for this trial, continual safety monitoring will be provided by the DSMC. The study will be stopped if at any time the following *combination* of conditions occurs, which is: at least 2 patients undergoing study therapy experience grade

≥ 3 toxicities related to study drug resulting in discontinuation, *and* the proportion of patients experiencing these toxicities exceeds 15%. With this rule, if the true proportion of patients experiencing these toxicities is 2%, which is considered acceptable, the probability of stopping accrual is 0.03. If the true proportion of patients experiencing these toxicities is 20%, which is considered unacceptable, the probability of stopping accrual is 0.88.

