16.3 Data and Safety Monitoring Plan

A Data and Safety Monitoring Committee (DSMC) is established at Huntsman Cancer Institute (HCI) to ensure the well-being of patients enrolled on Investigator Initiated Trials that do not have an outside monitoring review. The roles and responsibilities of the DSMC are set forth in the NCI-approved Data and Safety Monitoring (DSM) plan. The activities of the committee include reviewing adverse events (including SAEs), deviations, important medical events, significant revisions or amendments to the protocol, and approving cohort/dose escalations. If the DSMC and/or the PI have concerns about unexpected safety issues, the study will be

stopped and will not be resumed until the issues are resolved. The DSMC also reviews and approves audit reports generated by the Research Compliance Office.

This is a Phase II treatment study with no IND application classified as moderate risk per the NCI-approved DSM plan.

Each moderate risk study may be assigned a physician member of the DSMC as medical monitor, or in rare cases, an external medical monitor. The medical monitor will be notified of all serious adverse events (SAEs). SAEs occurring in patients treated at HCI or its affiliates will also be reviewed by the full DSMC monthly.

Each moderate-risk study will be assigned a dedicated research compliance officer who will monitor the trial. Moderate-risk trials will be monitored by RCO personnel after the first patient is enrolled and every six months thereafter during active enrollment. The RCO monitor will review the study status and summarize enrollment, toxicities, SAEs, dose escalation, statistical endpoints (e.g., stopping rules), deviations, etc. for the full DSMC membership at the regularly scheduled meetings. Amendments that increase risk, change dosing, or impact study objectives will be reviewed by the DSMC and approved by the PRMC and IRB. Moderate-risk trials will be formally reviewed by the DSMC after the first patient is enrolled and then semi-annually thereafter.

An initial audit of moderate-risk studies will be conducted by the RCO approximately one year after enrollment begins and annually thereafter. Audits of moderate-risk studies may be conducted more frequently as requested by the DSMC, IRB, PRMC, RCO management, or the PI.

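### The protocol gives the DSMC no route to by-arm data and no arm for the 15% stopping rule; if the count is pooled, the stated 0.88 chance of stopping does not hold for a harm confined to celecoxib

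*Combined protocol and SAP*

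**What the plan says.** Protocol section 4.2 (Randomization and Blinding) states that "only the Investigational Drug Services Pharmacy personnel at Huntsman Cancer Institute will know treatment assignments". It continues: "Access to unblinded data/documents will be controlled by the pharmacy to ensure the blind is maintained". The only unblinding route it sets out is emergency unblinding of a single patient, for which "the investigator has the sole responsibility for determining if the unblinding of a patient's treatment assignment is warranted". Neither the DSMC nor an unblinded statistician is named as a recipient of assignments.

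Section 12.3 (Stopping Rules) plans no interim analysis and gives ongoing safety monitoring to the DSMC. The trial stops, at any time, if two conditions hold together. At least two patients on study therapy must have a drug-related toxicity of grade 3 or worse that ends treatment, and "the proportion of patients experiencing these toxicities exceeds 15" percent. The stopping probability is given as 0.03 at a true rate of 2%. For the higher rate the section says: "If the true proportion of patients experiencing these toxicities is 20%, which is considered unacceptable, the probability of stopping accrual is 0.88". No arm, denominator or sample size is stated.

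The Study Summary describes the study product as celecoxib/placebo, and section 13.3.1 defines the toxicity population by one dose of study therapy, without regard to arm.

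Section 16.3 (Data and Safety Monitoring Plan) says what reaches the committee: "The RCO monitor will review the study status and summarize enrollment, toxicities, SAEs, dose escalation, statistical endpoints (e.g., stopping rules), deviations, etc". It does not say whether these summaries are pooled, split by masked arm, or unblinded.

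**The concern.** The stopping rule exists to catch unacceptable toxicity from celecoxib. The monitor who prepares the DSMC's summary is not pharmacy staff, and under section 4.2 only pharmacy staff know the arms. The rule's wording also covers placebo patients. Taken together, the literal reading is one count over both arms. With 1:1 allocation, a toxicity that occurs only on celecoxib then appears at half its true rate, while the 15% threshold stays where it is. A trial with an unacceptable rate on the drug could run on more often than section 12.3 leads the reader to expect. No other by-arm look is scheduled that would show the imbalance.

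**Working it through.** **Inputs from the protocol.** Stop if events x ≥ 2 and x/k > 0.15 after k patients; stated probabilities 0.03 at 2% and 0.88 at 20% (12.3). Allocation: "Patients will be randomized through the OnCore system in a 1:1 ratio between Arm 1 and Arm 2" (4.2). Size: "it is estimated that 53 patients will be randomized to result in 40 evaluable patients" (4.3), so 26-27 per arm randomized and 20 per arm evaluable. The Study Summary gives 60, or 30 per arm.

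**Input that is assumed.** The placebo rate of events meeting the rule is not in the documents; 0%, 2%, 5% and 10% are used.

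**Method.** Let f_k(x) be the probability of reaching patient k with x events and no stop so far. Then f_k(x) = f_{k-1}(x)(1 - p) + f_{k-1}(x-1)p. After each patient, the probability in any state with x ≥ 2 and x/k > 0.15 is moved to stopped. Since x/0.15 is 13.3, 20 and 26.7 for x = 2, 3 and 4, the trial stops on 2 events up to patient 13, 3 up to patient 19, 4 up to patient 26, and so on.

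**Step 1: reproduce the stated figures (same rate p in everyone counted).**

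| Patients counted | P(stop), p = 2% | P(stop), p = 20% |
|---|---|---|
| 20 | 0.028 | 0.833 |
| 26 or 27 | 0.029 | 0.879 |
| 30 | 0.029 | 0.890 |
| 40 | 0.029 | 0.924 |
| 53 | 0.029 | 0.950 |
| 60 | 0.029 | 0.956 |

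The 0.03 fits every size. The 0.88 is matched within two percentage points only for 25-31 patients, which is about one arm of 53 or of 60. A single look at the end does not reproduce the pair: it gives 0.00 at 2%, not 0.03. The stated figures therefore presuppose a check after every patient.

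**Step 2: pool both arms, with 20% on celecoxib.** Under independent 1:1 assignment each patient has event probability (0.20 + p0)/2, where p0 is the placebo rate. The dilution factor is 0.20 divided by that value.

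| Placebo rate (assumed) | Pooled rate | Dilution | P(stop), N=40 | P(stop), N=53 | P(stop), N=60 |
|---|---|---|---|---|---|
| 0% | 10% | 2.0 | 0.485 | 0.502 | 0.506 |
| 2% | 11% | 1.82 | 0.551 | 0.572 | 0.578 |
| 5% | 12.5% | 1.6 | 0.643 | 0.671 | 0.678 |
| 10% | 15% | 1.33 | 0.771 | 0.805 | 0.814 |

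**Step 3: sensitivity to entry order.** With strictly alternating arms at N = 53, 0% on placebo gives 0.467 (placebo first) to 0.525 (celecoxib first), and 2% gives 0.548 to 0.593. The range at 0-2% is thus 0.47-0.59.

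**Step 4: chance of missing a 20% celecoxib rate.** Stated: 1 - 0.88 = 0.12. Pooled, N = 53: 1 - 0.502 = 0.50 at 0% on placebo, 1 - 0.572 = 0.43 at 2%, 1 - 0.671 = 0.33 at 5%, and 1 - 0.805 = 0.195 at 10%. With no placebo events, the celecoxib rate would have to be about 34% before pooled counting of 53 patients stopped with probability 0.88.

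**The case against.** A reader might infer that the DSMC does pool the arms and cannot see an imbalance. The documents do not establish that. Section 4.2 has the pharmacy control access to unblinded data, and this could be extended to the DSMC. Section 16.3 refers the committee's role to an institutional monitoring plan that is not among the documents. What is shown is that the protocol grants no access and describes no by-arm report.

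A reader might also infer from the match at 26-27 patients that the rule was designed for the celecoxib arm. That is plausible but unproven, because section 12.3 gives no sample size. If it is so, the protocol names nobody outside the pharmacy who could count that arm. If both arms were meant, 0.88 does not describe a harm confined to the drug. Reconciliation is needed either way.

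A halved rate is the extreme case, not the general one. Relatedness is judged under the blind in patients having major surgery and radiation, and Table 3 acts even on possibly related events, so placebo patients may contribute. At 5-10% on placebo much of the loss disappears, though the result stays below 0.88.

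The 15% rule is also not the only protection. The full DSMC reviews SAEs monthly, the medical monitor is told of every SAE, and safety concerns of the DSMC or the principal investigator can halt the study (16.3). These safeguards stand, but they are partial: single blinded cases do not show a difference between arms.

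Finally, wider access has a real cost. The medical monitor may be a DSMC member (16.3), the monitor and sometimes the DSMC approve prohibited therapies for individual patients (7.3.2), and the safety and monitoring committee took part in the review that changed the sample size (13.2.1). This objection holds and shapes the fix.

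**Conclusion.** The point holds as an unresolved gap between sections 4.2, 12.3 and 16.3, with a measurable consequence. Followed literally, the plan leaves only a pooled count, and under that count the stated 0.88 is not the probability of stopping for a 20% rate confined to celecoxib. At 53 patients with independent 1:1 assignment it is about 0.50 to 0.57 for placebo rates of 0-2%, rising to 0.67 at 5% and 0.805 at 10%. These figures rest on the assumed placebo rates, on a check after every patient, and on pooling, which is inferred from the access rule and the arm-neutral wording. They do not support saying that the DSMC is barred from arm-level data, or that the apparent rate is always halved.

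**What to change.** Reconcile the three sections in one amendment.

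- **4.2 and 16.3:** allow the DSMC, in closed session, to receive from the pharmacy at each scheduled review the by-arm counts of patients treated, section 12.3 events, SAEs and deaths. Tie the report to scheduled reviews and not to single events, since an event-triggered table would reveal the affected patient's arm. Investigators, study staff and the monitor's summary stay blinded.
- **12.3:** state which denominator the 15% proportion uses, and the sample size and checking schedule behind the quoted probabilities. A count of the celecoxib arm, checked after every patient, gives about 0.88 at 26-27 patients and 0.83 at 20, with the false-stop probability at 2% still about 0.03. If pooled counting is intended, restate 0.88 for that count, with the placebo rate assumed.
- **Separation of roles:** DSMC members who act as medical monitor, approve individual patients' therapies, or join design or sample-size reviews should not receive the by-arm report.

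The cost is a few sentences and a short pharmacy table per review. The downside is a somewhat wider circle with access to arm data, which the closed session and the role separation are meant to contain.
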